9.2.2 Study population

Inclusion criteria:

- At least oneprescriptions for Tio/Olo combined inhaler or a LABA/ICS combined inhaler between 1st January 2014 and 31st December 2019.
 - a) The first dispensing of either Tio/Olo or LABA/ICS combined inhaler will be defined as the index date;
 - b) For the main analyses, only fixed dose combination (FDC) inhalers will be included.
- 2. Aged \geq 40 years on the index date
- 3. At least one diagnosis of COPD at any time prior to or on the index date;
- At least one year of continuous medical and health insurance plan prior to the index date will be required to allow for a look-back period for the covariates and identification of new use of the study drugs;
- 5. At least one record in the health insurance system database;

Exclusion criteria:

- 1. Any use of Tio/Olo, ICS/LABA, or ICS/LAMA/LABA in free or fixed form for one year prior to the index date;
- Individuals with asthma, allergic rhinitis, lung cancer, interstitial lung disease, or lung transplant identified at any time prior to the index date

NIS Protocol Page 24 of 48 BI Study Number: 1237-0110 c38660249-01

Proprietary confidential information © 2022 Boehringer Ingelheim International GmbH or one or more of its affiliated

For the analysis of the primary outcome, individuals will be followed up from the index date until the earliest of the date of: the follows, whichever first 1) moderate or severe COPD exacerbation; 2) disenrollment; 3) the end of the study period; 4) death; 5) discontinuation of the index drug use as a lapse of 1.5 months without subsequent prescription (except for switching from the index ICS/LABA to a different ICS/LABA); 6) adding ICS mono on top of Tio/Olo, or adding LAMA momo on top of the index ICS/LABA

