### **(1). Time to triple therapy escalation after index date**

Triple therapy escalation, defined as any LAMA/LABA/ICS fixed dose combination or any concurrent use for 30 consecutive days of the following:

- a. any LAMA/LABA fixed dose combination + any ICS single formulation
- b. any LAMA single formulation + any LABA/ICS fixed dose combination
- c. any LAMA single formulation + any LABA single formulation + any ICS single formulation

The event date will be the 30th day after initiation of triple therapy.

As time-to-event data, the analysis will be univariate proportional hazard regression analysis to estimate the hazard ratio (Tio/Olo vs. comparator) and its 95% CI.

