### **(2). Incidence rate of triple therapy initiation (first event per patient)**

Triple therapy escalation, defined as any LAMA/LABA/ICS fixed dose combination or any concurrent use for 30 consecutive days of the following:

- a. any LAMA/LABA fixed dose combination + any ICS single formulation
- b. any LAMA single formulation + any LABA/ICS fixed dose combination
- c. any LAMA single formulation + any LABA single formulation + any ICS single formulation

For incidence rates, it will be calculated for each cohort as follows:

Incidence rate among the Tio+Olo cohort = (total number of patients in the Tio+Olo cohort experiencing an event of interest for the first time during the given time period) / (total person-time at risk from current use of Tio+Olo during the given period)

Incidence rate among the comparison cohort = (total number of patients in the comparator LABA/ICS cohort experiencing an event of interest for the first time during the given time period) / (total person-time at risk from current use of comparator LABA/ICS during the given period)

The incidence rate ratio (IRR) and incidence difference for the outcome in the Tio+Olo - exposed group relative to that in the comparator group will be derived as follows:

Incidence rate ratio = incidence rate from the Tio+Olo cohort divided by the incidence rate from the matched comparator cohort.

Incidence difference = incidence rate from the Tio+Olo cohort – incidence rate from the matched comparator cohort

The IRR and their 95% CIs will be calculated using univariate negative binomial model. Incidence differences and their 95% confidence intervals will also be derived.

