Note that per study protocol, switching from one ICS/LABA to another ICS/LABA is not a censoring event.

Univariate proportional hazard regression model will be used to compare the time to event between the two treatment groups. It will provide an estimate of the hazard ratio (HR) of time to the first moderate or severe COPD exacerbation associated with Tio+Olo use relative to LABA/ICS use, along with 95% CI. In the event that there are baseline covariates with unequal distribution between the treatment groups, defined as absolute standardized difference larger than 0.1, the covariate(s) will be included in a multiple regression model in addition to the exposure status (Tio/Olo or LABA/ICS).

The analysis of the secondary objectives related to time to triple therapy escalation and time to first hospitalization for community-acquired pneumonia will be univariate proportional hazard regression model with an as-treated approach, similar to that of the primary analysis. The estimate of hazard ratio (HR) of time to triple therapy escalation and first hospitalization for community-acquired pneumonia associated with Tio+Olo use relative to LABA/ICS use,

[figure not shown]
Proprietary confidential information © 2022 Boehringer Ingelheim International GmbH or one or more of its affiliated companies

along with 95% CI will be provided. For the analysis of these time-to-event outcomes, patients will be followed until the event of interest or earliest of the date of the follows, whichever happened first:

- 1) outcome event of interest;
- 2) disenrollment;
- 3) the end of the study period;
- 4) death;
- 5) discontinuation of index drug use (a lapse of 45 days without subsequent prescription)
- 6) switching from Tio/Olo to ICS/LABA or from ICS/LABA to Tio/Olo

In the event that there are baseline covariates with unequal distribution between the treatment groups, defined as absolute standardized difference larger than 0.1, the covariate(s) will be included in a multiple regression model in addition to the exposure status (Tio/Olo or LABA/ICS).

[figure not shown]
Proprietary confidential information © 2022 Boehringer Ingelheim International GmbH or one or more of its affiliated companies

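### Dating every triple-therapy escalation 30 days after it starts lets the 45-day discontinuation rule censor some or all switches to a fixed-dose triple inhaler, depending on how the lapse is counted and dated

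*SAP*

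**What the plan says.** SAP 7.2.2(1) defines the outcome: "Triple therapy escalation, defined as any LAMA/LABA/ICS fixed dose combination or any concurrent use for 30 consecutive days of the following", followed by three free combinations. The 30-day condition belongs to concurrent use, so a fixed-dose triple inhaler qualifies on its own. The section then gives one dating rule for all routes: "The event date will be the 30 th day after initiation of triple therapy".

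SAP 10.1 sets follow-up for this outcome: "patients will be followed until the event of interest or earliest of the date of the follows, whichever happened first". One of the listed reasons is "discontinuation of index drug use (a lapse of 45 days without subsequent prescription". The only exemption stated in 10.1 is that "switching from one ICS/LABA to another ICS/LABA is not a censoring event". Nothing comparable is said about a move to a triple inhaler.

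Protocol 9.7.1 also lists discontinuation as an end of follow-up for this outcome, without a gap length. Protocol 9.2.2 gives the gap, for the primary outcome, as "discontinuation of the index drug use as a lapse of 1.5 months without subsequent prescription". Neither document says whether the lapse runs from the last prescription or from the end of its supply, or whether a discontinuation is dated at the end of the lapse or back-dated.

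SAP Appendix 3 lists the triple inhalers (R03AL08, R03AL09) as a group separate from both index drugs, so dispensing one is not a further index prescription.

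**The concern.** A fixed-dose triple contains all three drug classes, so a patient who receives one would ordinarily stop collecting the index inhaler. The same act that constitutes the outcome therefore sets off the discontinuation rule. The event has to wait until 30 days after the triple starts, while the lapse is measured from an index prescription or its supply. If the lapse ends first, the patient leaves the risk set as censored although the outcome has happened.

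That censoring is informative because the outcome itself causes it. It also depends on the route of escalation. A patient who adds an ICS to Tio/Olo, or a LAMA to ICS/LABA, keeps refilling the index inhaler and is counted. A patient who moves to a single triple inhaler may not be. If the two arms use these routes in different proportions, the hazard ratio partly reflects the route and not only the rate of escalation.

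**Working it through.** The plan gives no event count, power or expected frequency for this outcome, so there is no figure to reproduce. The check is date arithmetic.

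Inputs:
- Day 0 = last index prescription.
- S = days of supply. Not given in the documents; assumed 28 to 30.
- s = day on which the fixed-dose triple is first dispensed.
- Event day = s + 30 (SAP 7.2.2(1)).
- Lapse = 45 days (SAP 10.1).

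Four readings of the discontinuation date are possible:
- (a) 45 days from last prescription, dated at end of lapse: day 45.
- (b) 45 days from end of supply, dated at end of lapse: day S + 45, that is 73 to 75.
- (c) Back-dated to end of supply: day S, that is 28 to 30.
- (d) Back-dated to last prescription: day 0.

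The event is counted when s + 30 falls before the discontinuation date:
- (a) s + 30 < 45, so s < 15. Day 15 is a tie; later starts are censored.
- (b) s + 30 < S + 45, so s < S + 15. Starts more than 15 days after end of supply are censored.
- (c) s + 30 < S needs s < 0 when S is at most 30. Every start from day 1 on is censored.
- (d) s + 30 < 0 is impossible. All are censored.

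Results for S = 30:

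| Triple starts (day) | Event day | (a) day 45 | (b) day 75 | (c) day 30 | (d) day 0 |
|---|---|---|---|---|---|
| 10 | 40 | counted | counted | censored | censored |
| 15 | 45 | tie | counted | censored | censored |
| 16 | 46 | censored | counted | censored | censored |
| 30 (refill visit) | 60 | censored | counted | censored | censored |
| 45 | 75 | censored | tie | censored | censored |
| 46 | 76 | censored | censored | censored | censored |

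With S = 28 the pattern is the same. A refill-visit switch has its event on day 58, against days 45, 73, 28 and 0, and the tie under (b) moves to day 43.

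Under (a) and (b), starts 16 to 44 days after the clock begins fall before the lapse is complete. The plan's own rule still treats these patients as on the index drug when they escalate, yet their escalations are censored.

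Check of the remedy. If the fixed-dose triple is dated at first dispensing (day s), a refill-visit switch on day 28 to 30 precedes day 45 under (a) and day 73 to 75 under (b), so it counts. Under (c) it ties with day S, and under (d) it is still censored. Re-dating alone is therefore not enough; a precedence rule is also needed.

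**The case against.** **Thirty days is shorter than 45, so the event should come first.** This does not hold, because the two periods start on different days.

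**The 45 days may run from end of supply.** This stands in part. The gap rule that SAP 7.3 spells out for antibiotic and steroid courses counts from the end of supply. If the index drug is handled likewise and discontinuation is dated at the end of the lapse, a prompt switch at the refill visit is counted. But that rule is written for other drugs, and even then later starts within the lapse are lost. A reader might infer that all fixed-dose triple escalations are lost and that the outcome rests mainly on free add-ons. The documents do not support that: the loss is total, or essentially so, only if discontinuation is back-dated, and no frequency of fixed-dose triple use or coverage date is given.

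**A numerical bias cannot be claimed.** This stands. If every fixed-dose escalation were lost and there were no true difference, the observed hazard ratio would be about (1 − a)/(1 − b), with a and b the fixed-dose shares of escalations in the Tio/Olo and ICS/LABA arms. Shares of 50% and 30% would give 0.5/0.7 = 0.71; the reverse would give 0.7/0.5 = 1.40. Those shares have no source, and with no loss the ratio stays at 1.0. The figures only show that either direction is possible.

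**The incidence rate is a separate outcome.** This stands. SAP 7.2.2(2) repeats the definition but not the day-30 date, and the follow-up lists in 10.1 are introduced for the time-to-event outcomes and for rescue medication. A reader might also infer that each event adds up to 30 days on triple therapy to the denominator. The stated denominator, "total person-time at risk from current use of Tio+Olo during the given period", would on its plain words exclude time after the index inhaler has been replaced.

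**The plan separates the two concepts, and details may lie elsewhere.** For the primary outcome, 10.1 lists discontinuation and triple escalation as distinct reasons. It does not rank them where escalation is the outcome. The separate data management and review plan may hold operational detail, but it is not among the documents, and the dating rule in the SAP would still need changing.

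**Conclusion.** The point holds for one secondary outcome, time to triple-therapy escalation. The stated event date and the stated end of follow-up together censor some or all fixed-dose triple escalations under each of the four readings. The extent runs from only those started more than 15 days after supply ends to every one. This rests on two assumptions: the triple inhaler replaces the index inhaler, and a prescription covers 28 to 30 days.

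The incidence rate of triple initiation is affected only if it uses the same event date and follow-up rules, which the SAP does not state. For the primary outcome no event is lost by this route, since escalation and discontinuation are both censoring reasons there.

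The SAP should be corrected before the analysis. The documents do not allow a statement of how many escalations would be lost or which arm would be favoured.

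**What to change.** In SAP 7.2.2(1), date escalation by a fixed-dose triple inhaler at its first dispensing, and keep the day-30 date for free combinations only.

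In SAP 10.1:
- State whether the 45-day lapse starts at the last index prescription or at the end of its supply, and which date a discontinuation receives.
- State that, for the triple-escalation outcomes, a triple start before the lapse is complete is an event and takes precedence over discontinuation. This should cover the fixed-dose triple and any free combination that replaces the index inhaler and goes on to meet the 30-day condition (for example, three single inhalers), because the same collision arises there.

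In SAP 7.2.2(2), state the same event date and end person-time on it.

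The cost is a few sentences of SAP text and a small programming change. No new data are needed, and nothing in patient management changes.

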### **(2). Incidence rate of triple therapy initiation (first event per patient)**

Triple therapy escalation, defined as any LAMA/LABA/ICS fixed dose combination or any concurrent use for 30 consecutive days of the following:

- a. any LAMA/LABA fixed dose combination + any ICS single formulation
- b. any LAMA single formulation + any LABA/ICS fixed dose combination
- c. any LAMA single formulation + any LABA single formulation + any ICS single formulation

For incidence rates, it will be calculated for each cohort as follows:

Incidence rate among the Tio+Olo cohort = (total number of patients in the Tio+Olo cohort experiencing an event of interest for the first time during the given time period) / (total person-time at risk from current use of Tio+Olo during the given period)

Incidence rate among the comparison cohort = (total number of patients in the comparator LABA/ICS cohort experiencing an event of interest for the first time during the given time period) / (total person-time at risk from current use of comparator LABA/ICS during the given period)

The incidence rate ratio (IRR) and incidence difference for the outcome in the Tio+Olo - exposed group relative to that in the comparator group will be derived as follows:

Incidence rate ratio = incidence rate from the Tio+Olo cohort divided by the incidence rate from the matched comparator cohort.

Incidence difference = incidence rate from the Tio+Olo cohort – incidence rate from the matched comparator cohort

The IRR and their 95% CIs will be calculated using univariate negative binomial model. Incidence differences and their 95% confidence intervals will also be derived.

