The incidence rate ratio (IRR) for the triple therapy initiation in the Tio+Olo - exposed group relative to that in the comparator group, along with 95% CIs will be derived using univariate negative binomial model. In the event that there are baseline covariates with unequal distribution between the treatment groups, defined as absolute standardized difference larger than 0.1, the covariate(s) will be included in a multiple regression model in addition to the exposure status (Tio/Olo or LABA/ICS).

For annualized rate of moderate or severe COPD exacerbations and annualized rate of prescriptions of rescue medications, the ratio of Tio+Olo – exposed group relative to LABA/ICS group, along with 95% CIs will be derived using negative binomial model. In the event that there are baseline covariates with unequal distribution between the treatment groups, defined as absolute standardized difference larger than 0.1, the covariate(s) will be included in a multiple regression model in addition to the exposure status (Tio/Olo or LABA/ICS).

SAS codes for negative binomial model are provided in Annex.

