## Appendix 1. SAS code template for negative binomial model in the analysis of the secondary outcomes of interest

The following codes are provided by Boehringer Ingelheim statistician

```
PROC GENMOD DATA=test;
CLASS treat (ref='LABA/ICS') cova_cat;
MODEL ep_count = treat cova_cat cova_con /
DIST=negbin LINK=LOGTYPE3 OFFSET=logt;
LSMEANS treat / DIFF CL;
ESTIMATE 'Treatment effect on ratio-scale' treat 1 -1 / EXP;
RUN;
```

(In the model,  
treat: Tio+Olo group OR LABA/ICS group;  
Cova\_cat: categorical covariates;  
Cova\_con: continuous covariates)

For univariate analysis, Cova\_cat and Cova\_con are not applicable.

For calculating incidence rate ratio with 95% CI of triple therapy initiation (Tio+Olo vs. LABA/ICS),  
ep\_count (response): 1 (triple therapy initiation occurred per patient) or 0 (triple therapy initiation not occurred per patient);  
logt: nature log of the time at risk (first event per patient)

For calculating ratio (with 95% CI) of annualized rate of moderate or severe COPD exacerbations and annualized rate of prescriptions of rescue medications (Tio+Olo vs. LABA/ICS),  
ep\_count (response): number of events per patient  
logt: nature log of the time at risk per patient

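### The incidence rate ratio for triple-therapy initiation is defined as a quotient of two first-event rates, but is estimated with a negative binomial model that need not return that quotient

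*SAP*

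**What the plan says.** SAP 7.2.2 (2) builds each rate from patients with a first event over on-treatment person-time. The numerator for the Tio/Olo cohort is the "total number of patients in the Tio+Olo cohort experiencing an event of interest for the first time during the given time period" and the denominator is the "total person-time at risk from current use of Tio+Olo during the given period". The ratio is then defined outright: "Incidence rate ratio = incidence rate from the Tio+Olo cohort divided by the incidence rate from the matched comparator cohort". SAP 10.1 repeats these definitions, and protocol 9.7.1 gives the same ones.

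The estimator is a model. SAP 7.2.2 (2) says: "The IRR and their 95% CIs will be calculated using univariate negative binomial model". SAP 10.1 says that "The incidence rate ratio (IRR) for the triple therapy initiation in the Tio+Olo - exposed group" relative to the comparator, "along with 95% CIs will be derived using univariate negative binomial model". Protocol 9.7.1 also names a negative binomial model for this IRR.

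Appendix 1 leaves no doubt about the coding. The response is "1 (triple therapy initiation occurred per patient) or 0 (triple therapy initiation not occurred per patient", and the offset is the "nature log of the time at risk (first event per patient". The same template, with the negative binomial distribution, serves the two recurrent-count outcomes.

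The incidence difference is defined from the two crude rates. Table 4 sets out the number with events, person-years, both rates, the IRR, an adjusted IRR and the incidence difference side by side.

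**The concern.** A negative binomial model is normally chosen because patients contribute varying numbers of events, so that counts vary more than a Poisson model allows. Here each patient contributes one event at most, so that reason is absent. The dispersion parameter stays in the model all the same, and when it is positive it changes the treatment coefficient.

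What is at stake is one named secondary objective. A reader who divides the two rates in Table 4 may not obtain the IRR printed beside them. The confidence interval would then belong to a quantity that the SAP did not define, next to an incidence difference that comes from the crude rates. The SAP gives no reason for a dispersion parameter on this outcome and no rule for an estimate at zero.

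**Working it through.** The documents state no figure for this IRR, so there is none to reproduce. The check is algebra, followed by simulation under stated assumptions.

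**1. Poisson with log-time offset, treatment only.** With μ = λt, the score equation in each arm is Σ(y − μ) = 0, so the fitted rate is events divided by person-time. The exponentiated treatment coefficient is exactly the ratio that the SAP defines.

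**2. Negative binomial with dispersion k, same offset.** The score equation is Σ[(y − μ)/(1 + kμ)] = 0. At k = 0 this is the Poisson equation. For k > 0 patients with longer time at risk get less weight, and the solution generally differs from events over person-time.

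**3. What k measures when y is 0 or 1.**
- P(0) = (1 + kλt)^(−1/k).
- P(1) = λt(1 + kλt)^(−1/k − 1).
- Apart from the factor t, which holds no parameter, these are the survivor function and density of an exponential model with gamma frailty of variance k. The implied population hazard is λ/(1 + kλt), which falls over time.
- So k is learned only from how the observed hazard falls, and the treatment coefficient is a rate ratio conditional on the frailty.
- At k = 0 the score for k is Σ(μ²/2 − yμ). Under a constant hazard its mean is zero, so k should be estimated at zero in about half of data sets. If events come late (a rising hazard or a delayed event date), the score is negative and k stays at zero.

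**4. Single simulated data sets.** Assumptions: 2,489 per arm (the protocol 9.5 figure, used only for scale), comparator escalation rate 0.4 per person-year before heterogeneity, true ratio 0.7. The Poisson ratio is shown by hand; its interval uses SE(log ratio) = √(1/d₁ + 1/d₀), where d₁ and d₀ are the events per arm.

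- No heterogeneity: (511/1726)/(636/1641) = 0.2961/0.3876 = 0.764. SE = √(1/511 + 1/636) = 0.0594, interval 0.680 to 0.858. The negative binomial fit gives the same ratio and interval, with k about 0.
- Heterogeneity variance 4: (330/1857)/(407/1812) = 0.1777/0.2246 = 0.791. SE = √(1/330 + 1/407) = 0.0741, interval 0.684 to 0.915. The negative binomial fit gives 0.738 (0.620 to 0.878), with k = 3.785.

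**5. Averages over repeated data sets.** Assumptions: 2,489 per arm, 14-18% with an event, on-treatment censoring, a simulated advantage for Tio/Olo. The 30-day lag reflects SAP 7.2.2 (1), which dates escalation to the 30th day; 7.2.2 (2) does not repeat that rule.

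| Assumed hazard | Defined ratio | Negative binomial | Fitted / defined |
|---|---|---|---|
| Constant, no lag (k near zero in half of runs) | 0.797 | 0.795 | 0.997 |
| Weibull shape 0.8, lag | 0.737 | 0.722 | 0.980 |
| Weibull shape 0.6, lag | 0.749 | 0.695 | 0.928 |

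With a constant hazard and the lag, k was zero in every run and the two ratios were identical.

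For scale, the standard deviation of the log defined ratio in a similar set of runs was about 0.07 to 0.08. The log gaps are ln(0.737/0.722) = 0.021 and ln(0.749/0.695) = 0.075, or roughly a quarter of one standard deviation and one standard deviation.

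**6. Unequal time on drug, no true effect.** Under a falling hazard with shorter Tio/Olo persistence, the defined ratio averaged 1.13 and the negative binomial ratio 1.02. Under heterogeneity variance 4 with mean time on drug of 1.5 years for Tio/Olo and 0.5 for the comparator, they averaged 0.764 and 1.005, a factor of 1.005/0.764 = 1.32. The gap can go either way.

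**The case against.** The strongest reply is that the Poisson ratio is not the better measure of treatment effect. Step 6 bears this out: with a falling hazard and unequal time on drug, the crude rate ratio departs from 1 when there is no effect, while the negative binomial ratio stays near 1. This stands as a caution about the quantity the SAP chose. It does not justify the planned model, because the SAP does not ask for a frailty-conditional ratio here, and the Cox hazard ratio for the same event is already planned in Table 3. Nor is the negative binomial ratio uniformly better: in a run with a true hazard ratio of 0.75, shape 0.6 and the lag, it gave 0.69.

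A second reply is that Table 6 has the same feature, since negative binomial ratios sit beside events over person-years. That is fair as a point about presentation. But SAP 7.2.2 (4) and (5) define those ratios through the model rather than as a quotient, and repeat counts do inform the dispersion there. An adjusted IRR would not equal the crude quotient under a Poisson model either; the argument concerns the unadjusted IRR.

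Third, the gaps under equal persistence are within sampling noise or about equal to it. This is correct, and it limits the weight of the point.

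A reader might infer that the planned model never returns the defined ratio, or that the dispersion is always zero unless the hazard falls. Neither follows. At zero dispersion the two ratios coincide, and under a constant hazard without the lag the estimate is near zero in only about half of data sets.

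**Conclusion.** The SAP's definition and its estimator do not match for this outcome. That much follows from the text and the algebra. Whether the printed IRR differs from the quotient of the printed rates depends on the data: not at all when the dispersion is estimated at zero, by about 2% under a mildly falling hazard, by about 7% under a steeper one, and by up to about 30% in either direction in the more extreme simulations with unequal time on drug. These sizes rest on assumed hazards, event proportions and persistence, none of which the documents supply.

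The point covers one secondary measure. A reader might extend it to the negative binomial model in general or to the main result. The documents do not support either: the recurrent-count outcomes suit that model, and the primary outcome and the hazard ratio for escalation come from proportional hazards models. The change is worth making because it is cheap and removes an internal inconsistency.

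**What to change.** For triple-therapy initiation only, replace DIST=negbin with DIST=poisson, keep the log person-time offset, and preferably use a robust variance. Make the change in SAP 7.2.2 (2), SAP 10.1 and Appendix 1, and align protocol 9.7.1, which otherwise would conflict with the SAP. Keep the negative binomial model for rescue prescriptions and exacerbation counts.

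Add a sentence saying that the rate ratio can depart from 1 without a true effect if the hazard falls over time and time on drug differs by arm, so that Table 4 should be read beside the Cox hazard ratio in Table 3. State also whether the 30-day event date in SAP 7.2.2 (1) applies to 7.2.2 (2).

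If the sponsor prefers to keep the negative binomial model, the alternative is to redefine the IRR as the model ratio, say what is done when the dispersion is estimated at zero, and note under Table 4 that the IRR need not equal the quotient of the rates.

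The cost is a change to the model options in the SAS template and matching wording in two documents. No new data are needed.
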